- Social support evaluated by the evaluation protocol using the English Longitudinal Study of Ageing study. APGAR (including 5 questions).
- Quality of life evaluated using the Impact of Weight on the Quality of Life - Lite (IWQOL-lite) questionnaire including 31 questions.

Table 1: Questionnaires on hedonic response to food, addictive behaviour and mood state.

Hedonic response to food	Mood state, stress, negative emotions
DEBQ-external (10)	DEBQ-restraint and emotional (23)
Yale Food Addiction Scale II (25)	Positive and Negative Affect Schedule (PANAS) (20)
Binge eating scale (BITE) (33)	Barrat Impulsivity Scale (30)
Confounding variables	Alcohol Use Disorders Identification Test (AUDIT-4). Fagerström Nicotine Dependence Scale (6)
International Physical Activity Questionnaire (IPAQ) (7).	EPQR-neuroticism (23)
APGAR (5)	Hospital Anxiety and Depression Scale (14)
Quality of life evaluated with the Impact on Weight on the Quality of Life – lite questionnaire (IWQOL-lite) (31)	

Evaluation of food intake: The patients will also complete a registry of foods and drinks consumed over 3 days including a weekend day. It should include the type of food, cooking method, and portion size or weight. Afterwards, the total intake and by macronutrients will be analysed with the Diet Source software (Nestle Health Science. V4.0).

Primary variable:

Body weight: total weight lost (%), excess weight lost (%), total weight regained (%), excess of weight regain (%).

Data collection:

I. Additional information on demographic and anthropometric characteristics and on comorbidities both prior to BS and their evolution over time will be collected in an Excel datasheet designed with this objective and will include the following:

Centre: A number identifying each centre has been assigned starting at 1, with the first 9 numbers having a 0 before them.

REGAINSEEN

Versión 2, 07/03/2019

Code: To register the data of the patients a 5 digit code will identify each patient, with the first 2 numbers corresponding to the number assigned to the centre and the following 3 numbers will correspond to the number assigned to the patient upon entry in the study. For example, the first patient recruited in Hospital Clinic (corresponding to 04) will be assigned the code 001 so that the final code of this patient will be 04001. The code will be kept in each centre and confidentiality will be guaranteed by the investigator.

The Excel database will not include the number of the clinical history of the patient or any data which could identify the patient.

Study group: 0: control; 1: case

The investigator in each centre should register whether the number of the patient corresponds to a case or a control.

Age: in years

Sex: 0: man; 1 woman

Ethnicity: 0: Caucasian, 1: Gypsy; 2: Latin American; 3: other.

Marital status: 1. Married or with partner; 2. Single; 3. Separated/divorced; 4. Widow.

Lives with (number of people): 1. Alone; 2. Partner/husband/wife; 3. Children, number ...; 4. Parents; 5. Elderly parents/in-laws; 6. other

Occupation: 1. Homemaker; 2. Unskilled worker 3. Skilled worker. 4. Administrative, 5. Contract worker; 6. Retailer; 7. Business person; 8. Other.

Current occupational status: 1. Active/remunerated work; 2. Unemployed; 3. Retired; 4. Temporary work leave; 5. Permanent work leave; 6. Disability.

Level of education: The highest level of education achieved will be registered. 1. No education; 2.- primary; 3. secondary; 4. technical training or similar; 5. university; 6. other.

Comorbidities registered prior to surgery:

➤ Diabetes:

0: normal;

1: altered fasting glucose /intolerance to carbohydrates or previous gestational diabetes;

2: Type 2 diabetes;

3: Type 2 diabetes with HbA1c > 8% 4: insulin treatment.

If a patient classifies as more than one category, this should be separated with a comma. For example, the patient has type 2 diabetes treated with insulin + HbA1c > 8, this would be 2,3,4.

➤ Sleep apnoea

0: normal or Epworth score < 10;

1: Epworth > 10, apnoea-hypopnoea index 5-20;

2: Use of continuous positive airway pressure therapy (CPAP);

3: Cor pulmonale.

➤ Arterial hypertension (AHT):

0 Normotensive (blood pressure (BP) \leq 140/90 mmHg);

1: treatment with 1 hypotensive drug;

2: treatment with more than 2 drugs;

3: decompensated AHT > 140/90 mmHg.

➤ Dyslipidaemia:

0: no;

1: treatment with statins;

2: treatment with fibrates;

3: treatment with statins + fibrates.

➤ High-density lipoprotein (HDL) level \leq 40 mg/dl: 0: no, 1: yes.

➤ Previous cardiovascular events: 0: no; 1: yes .

Psychiatric disorder: 0: no; 1: yes. Add diagnosis.

Variables of weight: Weight in Kg and height in metres at baseline in the two groups; weight at 4, 12, 36 and 60 months in the intervention group and in the control group.

These data will be used to calculate the absolute WL, % of WL, EWL, BMI lost, the total weight regained (TWR) and the EWR .

Surgery: 0: GBP, 1: LSG

Date of surgery: This will be registered as a date and is in order to adapt the dates of the follow-up visits to the different times.

Follow-up: at 4-6 months, and 1, 3 and 5 years

Diabetes yes/no; diabetes treatment (0: no; 1: metformin, 2: DPP4 inhibition, 3: iSGLT2, 4: Sulfonylureas , 5: GLP-1 analogues, 6: insulin). Likewise, combined treatment

should be separated with a comma. For example, a patient controlled with metformin + iSGLT2 would be 1,3.

AHT yes/no; AHT treatment (0: no; 1: treatment with 1 drug; 2: treatment with > 2 drugs);

Dyslipidaemia: 0: No, 1: Yes; treatment: 0: no, 1: Treatment with statins, 2: treatment with fibrates, 3: treatment with statins + ezetimibe.

Sleep apnoea hypopnoea syndrome (SAHS) yes/no; Use of CPAP yes/no;

Revision surgery: 0: no, 1: yes.

Date of revision surgery: registered in date format.

Analytical parameters: fasting glucose, insulin, HbA1c, creatinine, total cholesterol, HDL.

Bioimpedance: fat mass (FM) %; FM kg; fat free mass: (whatever is available).

Sample size

The study will include 445 patients undergoing BS. It is estimated that the percentage of losses to follow-up at 5 years will not be greater than 10% and thus, at least 400 patients must achieve complete follow-up. This sample size will have a statistical power of 80% for detecting an effect size, that is, differences divided by the standard deviation of at least ≥ 0.281 [11]–[13] in magnitude; this effect size is considered in the literature as being of small magnitude [14], [15], and consequently the statistical power will be greater for greater magnitudes. The study will also be discriminatory for binary variables presenting an association with an odds ratio (OR) of at least ≥ 1.78 [11], [16], [17]. Finally, correlations ≥ 0.6 [18]–[21] will be detected considering that values < 0.5 are not relevant. In the three cases cited the calculations of sample size were made using a bilateral level of significance of 5% and a statistical power of 80%. This sample size will allow adjusting possible confounding factors and generate a multivariate model with a minimum number of covariates (at least 4-7, depending on the final number of events and correlations) to obtain adjusted estimators [22]–[24].

Additionally, 100 controls not undergoing BS will be included and matched for age, gender and BMI with the objective of standardising the values in the scales. The ratio will be 1:4 for controls and patients undergoing BS, respectively.

Statistical analysis

The design and statistical analysis of the present study meet the recommendations of consensus documents in the literature [25]–[28], specially the TRIPOD statement [29]. A statistical analysis plan (SAP) will be elaborated [30] prior to finalisation of data collection and will provide an in depth description of the statistical methods to be used, the tables and figures that will be included in the statistical report as well as the

strategy to follow in the case of missing values [31], [32], and multiplicity [33] adapted to regulatory [34] and scientific recommendations [26].

Descriptive statistics will be used according to standard calculation methods [35]. To elaborate a predictive model to a determined time, logistic regression models will be used [36]–[39]. For time variables up to a determined event, survival analysis techniques will be used. The function of survival as well as the median of time to the event (confidence interval of 95% [CI 95%]) will be estimated using the Kaplan-Meier method. Estimations of risk will be made with the classical [40] and extended [41] Cox proportional hazards model. Covariables will be tested for the assumption of proportional hazards. Initially all the possible covariables will be analysed in a univariate analysis, and factors with $p < 0.1$ will be included in a multivariate model. All the variables not selected for inclusion ($p \geq 0.1$) will, in turn, be checked in the final model to determine whether their inclusion would improve adjustment of the model by a p value < 0.1 or a value less than Akaike. Continuous variables will be tested as continuous linear variables, categorical variables (that is, quartile and predefined for clinical reasons) or continuous non-linear variables based on previously published literature, clinical value and goodness-of-fit models.

The following is a summary of the general approach of inferential statistical analysis. The Fisher exact test will be used to compare categorical variables. For continuous variables between the two groups, the Student's t test and ANOVA for more than two will be used. In the case of not fulfilling the assumptions of applicability or of ordinal variables, non-parametric methods (Mann-Whitney U test or Kruskall-Wallis) or an ANOVA will be used with previous transformation of the dependent variable to ranges to evaluate more than one factor concomitantly (rank-ANOVA).

Variables repeated over time will be analysed as follows: (i) continuous variables, such as the evolution of the variables of weight, with longitudinal mixed model for repeated measurements (MMRM)[42], [43]; (ii) Binary variables will be analysed using Generalised Linear Mixed Models (GLMM). Marginal models will be used (Generalised Estimating Equation (GEE) for the analysis of sensitivity [44][45].

The results will be analysed with the SAS version 9.4 statistical package (or a higher version) [46] (SAS Institute Inc., Cary, NC) or with equivalent validated software. The level of significance will be bilateral at 5%.

Ethical Committee

The protocol should be approved by the Ethical Committees of the participating centres. An informed consent sheet will be included together with the project for presentation to the Ethical Committee of each centre. Informed consent will include special emphasis on the confidentiality of the personal data and that these data will not be able to be identified. Following receipt of approval, the investigators must send a copy of the approval and the number assigned for incorporation in the project file. The original should remain in the centre and its safety is the responsibility of the centre investigator.

The results of the centres that do not obtain approval from the Ethical Committee will not be used in the analyses.

Treatment of missing data

Missing data will be registered in box x to ensure that the data cannot be recovered. If the box remains empty, there will continue to be doubt about whether the data can be recovered.

References

- [1] P. Bjorntorp *et al.*, "Obesity : Preventing and Managing the Global Epidemic," *WHO Tech. Rep. Ser.*, p. 253, 2000.
- [2] A. P. Courcoulas *et al.*, "Long-term outcomes of bariatric surgery: A National Institutes of Health symposium," *JAMA Surg.*, vol. 149, no. 12, pp. 1323–1329, 2017.

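### The hypertension codes skip exactly two drugs at baseline and follow-up, and the baseline sleep apnoea codes leave a gap above an index of 20 without CPAP.

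*Combined protocol and SAP*

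**What the plan says.** The Data collection section sets out an Excel datasheet in which information "on comorbidities both prior to BS and their evolution over time will be collected". The codes that matter here are these.

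- **Hypertension, prior to surgery.** Code 0 is "0 Normotensive (blood pressure (BP) \leq 140/90 mmHg"; code 1 is "1: treatment with 1 hypotensive drug"; code 2 is "2: treatment with more than 2 drugs"; code 3 is "3: decompensated AHT > 140/90 mmHg".
- **Hypertension, follow-up visits.** The item is "AHT yes/no; AHT treatment (0: no; 1: treatment with 1 drug; 2: treatment with > 2 drugs".
- **Sleep apnoea, prior to surgery.** Code 0 covers patients who are normal or score below 10 on Epworth. The next code is "1: Epworth > 10, apnoea-hypopnoea index 5-20". Code 2 is CPAP use and code 3 is cor pulmonale.
- **Sleep apnoea, follow-up visits.** Two yes/no items, one for the syndrome and one for CPAP, with no index bands.

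Under diabetes, the protocol allows several codes separated by a comma when a patient meets more than one. Neither the hypertension list nor the apnoea list has an other category, though ethnicity, occupation and education do.

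**The concern.** A code list should give every patient a place. These two do not, and the gaps come from what the rules say, not from detail left for later. A centre following the text has no correct entry for a patient on two antihypertensive drugs. It has none either for some patients with an apnoea index above 20 who do not use CPAP. Different centres could settle this differently.

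The Introduction gives comorbidities two roles: they may relapse with weight regain, and they are among the factors associated with weight loss and regain. The Statistical analysis section screens all possible covariables for the multivariate model. A miscoded baseline would distort the description of the cohort, the apparent change after surgery, and any adjustment that uses these fields.

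**Working it through.** No sample size, power or significance figure is involved. The check is whether each possible patient state meets at least one code, taking the definitions literally.

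**Hypertension.** Inputs: the baseline and follow-up lists quoted above. Rules applied: code 0 if blood pressure is at or below 140/90; code 1 if one drug; code 2 if more than two drugs; code 3 if blood pressure is above 140/90. At follow-up: 0 if no drug, 1 if one, 2 if more than two.

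| Drugs | Baseline codes met, BP ≤ 140/90 | Baseline codes met, BP > 140/90 | Follow-up treatment code |
|---|---|---|---|
| 0 | 0 | 3 | 0 |
| 1 | 0, 1 | 1, 3 | 1 |
| **2** | **0 only** | **3 only** | **none** |
| 3 or more | 0, 2 | 2, 3 | 2 |

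Code 0 is defined by blood pressure and not by treatment, so every controlled patient meets it. With one drug, or with three or more, a second code shows that the patient is treated. With two drugs nothing does, and the patient looks the same as someone without hypertension. Above 140/90 the disease is recorded through code 3, but the drug count is lost.

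Take a controlled patient on two drugs at baseline who is on one drug at a later visit. The literal record is code 0 at baseline, then hypertension yes with treatment code 1. A reduction in treatment reads as new disease. Moves from one drug to two, or from three to two, cannot be entered at all.

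**Sleep apnoea at baseline, index above 20.** Rules applied: code 0 if Epworth is below 10; code 1 if Epworth is above 10 and the index is 5 to 20 (the comma is read as requiring both); code 2 if CPAP; code 3 if cor pulmonale.

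| Epworth | Neither CPAP nor cor pulmonale | Cor pulmonale only | CPAP only | Both |
|---|---|---|---|---|
| Below 10 | **0 only** | 0, 3 | 0, 2 | 0, 2, 3 |
| Exactly 10 | **none** | 3 | 2 | 2, 3 |
| Above 10 | **none** | 3 | 2 | 2, 3 |

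The gap is confined to patients with neither CPAP nor cor pulmonale. With Epworth at 10 or more they have no code. With Epworth below 10 they share code 0 with normal patients.

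**Epworth of exactly 10, at any index.** Code 0 needs a score below 10 and code 1 a score above 10. A score of 10 meets neither, unless the patient is otherwise normal and enters code 0 that way.

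The comma rule does not help, because it combines existing codes and cannot supply a missing one.

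**The case against.** The strongest reply is that this is a wording slip in secondary fields, with little consequence. Much of that stands.

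- More than two may have been meant as two or more. That is plausible, but the gap appears once in words and once as a symbol, and nothing in the protocol settles the meaning. The datasheet itself is not among the documents, so whether its fields repeat the wording cannot be checked.
- Disease status is largely preserved. Follow-up keeps yes/no items for hypertension, the apnoea syndrome and CPAP. Code 3 catches two-drug patients above 140/90 at baseline, and the apnoea gap exists at baseline only. All of this is correct and limits the damage.
- No comorbidity is named as a confounder or endpoint. The objective concerns eating pattern, psychological variables and weight, and the primary variable is body weight. Use of comorbidities as covariates is only a possibility under the general screening rule.

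A reader might infer more than the documents support. One inference is that blanks are lost for good. The section on treatment of missing data reserves an x for values that cannot be recovered and treats an empty box as unresolved, and each centre keeps the patient code, so records can be traced. Another is that affected patients will drop out of the multivariate models. The protocol states no complete-case rule and leaves the strategy for missing values to a later SAP. A third is a head count. Any such number needs assumed rates of hypertension treatment and of two-drug use, and would still have to allow for patients whom code 3 captures.

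**Conclusion.** The point holds as a coding defect in secondary data fields. Exactly two antihypertensive drugs has no drug-count code at baseline or follow-up, and a controlled two-drug patient is literally recorded as normotensive before surgery. The baseline apnoea list has no code for an index above 20 without CPAP or cor pulmonale when Epworth is 10 or more, and merges such patients with normal ones when Epworth is below 10.

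The effect is limited to describing comorbidities, following their change and possibly adjusting for them. The weight variables and the sample size are unaffected. The size in patients cannot be computed, because the documents give no frequency for two-drug treatment or for an index above 20 without CPAP.

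The conclusion rests on a literal reading. If every centre took hypertension code 2 as two or more, no two-drug patient would be miscoded. If apnoea code 1 were read as meeting either condition, patients with Epworth above 10 and an index above 20 would fall into it alongside milder disease. The text directs neither reading.

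**What to change.** Make the lists exhaustive and consistent between visits:

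1. Hypertension: redefine code 2 as two or more drugs, at baseline and at follow-up, or add a separate code for exactly two at both.
2. Sleep apnoea at baseline: add a code for an index above 20 without CPAP.
3. Epworth: make one of the two boundaries at 10 inclusive.

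The cost is an edit to the code list and a note to centres. Centres that have already entered data recheck the affected fields against their records. Redefining code 2 means less rechecking: existing code 2 entries stay valid whether a centre read it as two or more or as more than two, so only the other entries and blanks need review. A separate code for exactly two keeps more detail but requires code 2 entries to be checked as well. This is a matter of data coding and changes nothing in patient management.

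### The only adjusted predictor models the plan specifies are event-based (logistic or Cox, on an unnamed yes/no status), although the primary variables are continuous percentages and the planned continuous models are given no scores or adjusters

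*Combined protocol and SAP*

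**What the plan says.** The Objective section asks how eating pattern and psychological variables relate to weight trajectory in the short and long term. The Primary variable section lists "Body weight: total weight lost (%), excess weight lost (%), total weight regained (%), excess of weight regain", each a percentage.

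The Statistical analysis section describes two kinds of model:

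- **Predictor models.** "To elaborate a predictive model to a determined time, logistic regression models will be used". Time to an event is handled by Kaplan-Meier and Cox. The covariate selection rule (univariate p < 0.1, then a check of the excluded variables by p value or Akaike) follows directly. No outcome status is named for either model. The section Weight variables: definitions gives cut-offs (excess weight lost above 50%, total weight lost above 25%, excess weight regain above 15%) but links them to no model.
- **Models and tests for continuous outcomes.** Repeated measures are assigned as "continuous variables, such as the evolution of the variables of weight, with longitudinal mixed model for repeated measurements (MMRM"). Two-group and multi-group comparisons use the t test, ANOVA, non-parametric tests or rank-ANOVA. No score, score-by-visit term or adjustment set is named for any of these.

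The Sample size section gives "The study will include 445 patients undergoing BS" and "at least 400 patients must achieve complete follow-up". It quotes power for "differences divided by the standard deviation of at least ≥ 0.281", for "binary variables presenting an association with an odds ratio (OR) of at least ≥ 1.78" and for a correlation. It then expects "a multivariate model with a minimum number of covariates (at least 4-7, depending on the final number of events and correlations").

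**The concern.** A question about a continuous trajectory is best answered by a model with the continuous percentage as outcome and the score as a predictor, adjusted for the declared confounders. No such model is written down. The models that do carry predictors and adjustment need a yes/no status, and the Sample size section ties the number of covariates to the number of events. The mixed model, as worded, describes how weight changes and not what is associated with the change.

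At stake is power for weak predictors. The Introduction says that earlier studies found inconclusive or weak relationships, so effects near the limit of detection are the ones that matter. With the status unnamed and three cut-offs available, the choice of cut-off could also be made after the data are seen.

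**Working it through.** **1. The plan's own figure.** Inputs from the Sample size section: 445 enrolled, 10% loss, 400 completers, effect 0.281 SD, two-sided 5%, power 80%. The split between compared groups is not stated; I assume 200 v 200.

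- Retention: 445 × 0.90 = 400.5, so about 400.
- Standard error of a standardised difference: √(2/200) = 0.100. Power = Φ(0.281/0.100 − 1.960) = Φ(0.85) = 0.80.

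The figure reproduces, for a continuous outcome.

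**2. The same effect as a correlation.** With 400 patients, Fisher's z requires atanh(r) × √397 = 1.960 + 0.842 = 2.802, so r = 0.14. Converting 0.281 SD at an equal split gives r = 0.281/√(0.281² + 4) = 0.139. So 80% power at r = 0.14 is the plan's continuous-outcome power on another scale.

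**3. Loss from cutting the outcome.** For a normal outcome and a small effect, a yes/no status held by a share p of patients keeps this fraction of the information:

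E = φ(z_p)² / [p(1 − p)]

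Power after the cut = Φ(2.802 × √E − 1.960). Detectable difference = 0.280/√E. The share p is not in the documents; 20% to 50% is an assumed range.

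| Share with status | E | Loss | 400 patients act like | Power (0.80 if uncut) | Detectable difference (SD) |
|---|---|---|---|---|---|
| 50% | 0.1592/0.25 = 0.637 | 36% | 255 | 0.61 | 0.35 |
| 30% | 0.1209/0.21 = 0.576 | 42% | 230 | 0.57 | 0.37 |
| 20% | 0.0784/0.16 = 0.490 | 51% | 196 | 0.50 | 0.40 |

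Rarer statuses cost more: the loss is 57% at 15% and 66% at 10%.

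**4. Cross-check against the plan's odds ratio.** Assume, which the plan does not say, that OR 1.78 refers to weight cut at its median in groups of 200. The two proportions are then 0.428 and 0.572, a probit difference of 0.361 SD. (0.281/0.361)² = 0.61, close to the 0.637 in the first row.

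**5. Limits.** The formula concerns a status at a set time. It does not carry over to Cox regression, which also uses the time of the event. Normality is doubtful for the two regain variables: regain is current weight minus nadir weight, so it cannot be negative, is zero for anyone at nadir, and has no meaning before nadir.

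**The case against.** The strongest reply is that continuous weight is not abandoned. The plan has a mixed model for weight over time, t test, ANOVA and a rank-ANOVA meant for several factors at once, and it is sized partly on a mean difference and a correlation. It never calls the logistic model the main analysis. It describes its inferential section as a summary and promises a detailed SAP, so silence on the mixed model's covariates is not a decision to leave them out. A yes/no question is also legitimate: the protocol predefines cut-offs and asks about patients with insufficient loss or regain.

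Most of this stands, and it rules out three stronger readings that a reader might infer:

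- **That scores are linked to weight only through yes/no models.** The continuous analyses above contradict this. What remains is that they carry no named score or adjuster.
- **That 4 to 7 covariates is a ceiling.** The text says at least 4 to 7, which is a floor.
- **That the declared confounders need more events than the study will have, for example 120 against 40 to 70.** Both figures come from a rule of ten events per variable, which the text does not state; one of the references it cites for this is about relaxing that rule. At 30% to 50% events, 400 patients supply 120 to 200 events in any case.

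The promised SAP does not remove the point. The protocol has already named logistic regression for prediction at a set time, and a more efficient method is available for the same data.

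**Conclusion.** The point holds as a choice of analysis that should be improved; it does not make the study invalid. The one adjusted route from scores to weight that the plan spells out is event-based, on an unnamed status, and the adjusted association with the continuous primary variables is left unspecified.

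The size is conditional. If the set-time association rests on the logistic model, if the outcome is roughly normal, and if 20% to 50% of patients have the status, then 36% to 51% of the information is lost and power at r = 0.14 falls from 0.80 to between 0.61 and 0.50. The loss is larger for a rarer status. Neither the event share nor the distribution is in the documents, so these figures should not be quoted as the plan's actual loss, nor applied to the Cox models or without caution to the regain variables.

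**What to change.** In the SAP, before data collection ends:

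- **Main analysis of the objective.** Use the mixed model already planned, on continuous percentage total (or excess) weight lost, with visit, score, score-by-visit and the declared confounders as fixed effects.
- **Single visits.** Use linear regression of the continuous percentage, with the same score and confounders.
- **Regain.** Analyse it as a continuous variable only at visits after nadir, with a method suited to a variable bounded at zero, such as the rank-based analysis already planned. Do not derive probabilities of crossing a regain threshold from a Gaussian model.
- **Logistic and Cox models.** Keep them as secondary clinical-threshold analyses, with the status tied in advance to the cut-offs in Weight variables: definitions.

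The cost is SAP wording and some extra modelling, with no new data. The small downside is that results are expressed first per percentage point of weight and only second as threshold risks.

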- a) Candidates to primary BS undergoing laparoscopic gastric bypass (LGBP) or laparoscopic sleeve gastrectomy (LSG) from September 2020 to September 2022. This group will be evaluated prior to surgery (a period vulnerable to biases by the request for surgery that affect the answers to the questionnaires for fear of being contraindicated for surgery). The subjects of this group will be followed at 4 months, 1 year, 3 years and 5 years after BS.
- b) A control group of subjects with obesity not candidates to BS matched with the intervention group for age, sex and BMI prior to BS.

*The control group will be recruited by each investigator (10 subjects) and will be evaluated once. According to our casuistic, in order to be comparable with the REGAINSEEN

Versión 2, 07/03/2019

intervention group 80% should be women of 45 years of age with a BMI $> 40 \text{ kg/m}^2$. This group is needed to adjust for variables such as motivation, patient expectations related to surgery and the effect of surgery.

Inclusion criteria:

- Candidate to primary BS from 09/2010 to 09/2021.
- Subjects with obesity ($\geq 40 \text{ kg/m}^2$) not candidates to BS.
- Internet users.
- Primary BS: LGBP and LSG.
- Accept to participate in the study and provide signed informed consent.

Exclusion criteria:

- Second time and/or revisional BS.
- Pregnancy.
- Presence of intellectual impairment impeding the administration of the psychometric tools.
- Type 1 diabetes.
- Dyslexia.

Weight variables: definitions.

- a) The different weight variables will be calculated as follows:
 - Weight lost (kg): Pre-BS weight – weight at nadir.
 - Current weight lost: Pre-BS weight - current weight.
 - Ideal weight: weight corresponding to a BMI = 25 kg/m^2 .
 - Excess weight lost (%): $(\text{Pre-BS weight} - \text{current weight})/\text{excess weight} [(\text{pre-BS weight} - \text{ideal weight}) \times 100]$.
 - Total weight lost (%): $(\text{pre-BS weight} - \text{current weight}/\text{pre-BS weight}) \times 100$.
- b) To study WR the following variables will be calculated:
 - Total WR (%): $(100/(\text{pre-BS weight} - \text{weight at nadir})) * \text{weight regained (kg)}$.
 - Excess WR (EWR %): $[(\text{current weight} - \text{weight at nadir})/\text{excess weight}] \times 100$
 - Weight regained (Kg): current weight – weight at nadir.

Excess weight lost $> 50\%$, total weight lost $> 25\%$ and Excess weight regain $> 15\%$ will be considered as significant.

Psychological evaluation:

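### The survival event is not named; if Kaplan-Meier and Cox are applied to a status seen only at visits, the median comes out late and, with common events, hazard ratios shrink

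*Combined protocol and SAP*

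**What the plan says.** The protocol's Statistical analysis section states: "For time variables up to a determined event, survival analysis techniques will be used". It then fixes the outputs: "the median of time to the event (confidence interval of 95% [CI 95%]) will be estimated using the Kaplan-Meier method", and "Estimations of risk will be made with the classical [40] and extended [41] Cox proportional hazards model". The event is not named there or elsewhere. No interval-censored method, discrete-time method or rule for tied times is mentioned. Detail is deferred: "A statistical analysis plan (SAP) will be elaborated [30] prior to finalisation of data collection".

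Under Data collection, the weights listed are "weight at 4, 12, 36 and 60 months in the intervention group and in the control group". Diabetes, hypertension, dyslipidaemia and sleep apnoea are recorded as status at each visit: "Follow-up: at 4-6 months, and 1, 3 and 5 years". None of these has an onset date. Revision surgery does: "Date of revision surgery: registered in date format". The date of the primary operation is also recorded.

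The section on weight definitions supplies a threshold that could serve as an event: "Excess weight regain $> 15\%$ will be considered as significant".

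For outcomes repeated over time, the plan gives MMRM for continuous variables, GLMM for binary ones and GEE as sensitivity analysis. It gives logistic regression for prediction at a fixed time.

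**The concern.** Standard Kaplan-Meier and Cox analyses treat the event time as known. That holds for revision surgery. A status seen only at visits is known to have started somewhere between the last negative visit and the first positive one, and after month 12 those visits are two years apart. If the first positive visit is entered as the event time, the median can only be a visit time or not reached. The confidence interval treats that date as exact, and Cox works with a few heavily tied times.

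This matters because regain is the study's main interest and has a ready binary definition. A published median time to regain could reflect the visit calendar more than the patients, and hazard ratios for psychological predictors could be too close to 1.

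**Working it through.** **Inputs from the protocol.** Visits at 4, 12, 36 and 60 months, so the gaps are 4, 8, 24 and 24 months. A missed 36-month visit widens the window to 60 − 12 = 48 months. The first follow-up is given as 4 months in one place and 4-6 in another, which does not change the 24-month maximum. There are 400 completers.

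**The plan's own figures.** 400/0.9 = 444.4, so 445, and 200 against 200 (an assumed equal split) at a standardised difference of 0.281 gives 80% power. Both reproduce, but neither concerns survival. The plan states no event rate, hazard ratio or median.

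**Assumptions, none from the documents.** A share p crosses the threshold by month 60 and stays across. All visits are attended. Onset is spread evenly over months a to b, or exponentially after a lag of L months.

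**Step 1, true median.** Even onset: t = a + (b − a) × 0.5/p. Exponential: λ = −ln(1 − p)/(60 − L) and t = L + ln 2/λ. Examples: 12 + 48 × 0.5/0.6 = 52.0; with L = 12 and p = 80%, λ = 1.609/48 = 0.0335 and t = 12 + 0.693/0.0335 = 32.7.

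**Step 2, visit-dated median.** It is 36 if at least half have crossed by month 36, otherwise 60.

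| Onset | p | True median | Crossed by 36 | Visit-dated | Late by |
|---|---|---|---|---|---|
| Even, 12-60 | 60% | 52.0 | 30.0% | 60 | 8.0 |
| Even, 12-60 | 70% | 46.3 | 35.0% | 60 | 13.7 |
| Even, 12-60 | 80% | 42.0 | 40.0% | 60 | 18.0 |
| Even, 12-48 | 60% | 42.0 | 40.0% | 60 | 18.0 |
| Even, 12-48 | 70% | 37.7 | 46.7% | 60 | 22.3 |
| Even, 12-48 | 80% | 34.5 | 53.3% | 36 | 1.5 |
| Exponential, L = 12 | 55% | 53.7 | 32.9% | 60 | 6.3 |
| Exponential, L = 12 | 60% | 48.3 | 36.8% | 60 | 11.7 |
| Exponential, L = 12 | 70% | 39.6 | 45.2% | 60 | 20.4 |
| Exponential, L = 12 | 80% | 32.7 | 55.3% | 36 | 3.3 |
| Exponential, L = 0 | 60% | 45.4 | 42.3% | 60 | 14.6 |
| Exponential, L = 0 | 80% | 25.8 | 61.9% | 36 | 10.2 |

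Nine of the twelve rows lie between 3 and 18 months. The other three have a true median just before or just after the 36-month visit.

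**Step 3, confidence interval** (4,000 simulated studies of 400, log-log limits).
- Even onset 12-60, p = 60, 70, 80%: the interval is 60 to 60 in 98, 100 and 97% of studies and covers the true median in 0, 0 and about 3%.
- Even onset 12-48: coverage is 2-3% at 60%, 77% at 70% and 0% at 80%. At 75% it is 98%, because the true median is then exactly 36.0.
- Exponential onset, p from 60 to 80%: coverage is 0 to about 55%.
- p = 45%: the median is not reached in 97-98% of studies, which is the correct answer.
- Actual dates varying by 2 months either way (300 studies), even onset 12-60: typical intervals are 59.7-60.7, 59.1-60.0 and 58.5-59.4, with coverage 0, 0 and 2%. Using real visit dates is no cure.

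**Step 4, Cox** (400 patients, binary covariate split 50/50, constant hazard from month 12, true hazard ratio 2.0).
- Nominal months, 28% events: Breslow 1.91 (coverage 96%), Efron 2.01.
- Nominal months, about 72% events: Breslow about 1.64 (coverage about 65%), Efron about 1.96.
- Dates varying by 2 months, about 72% events: about 1.85 with either, coverage about 89%.
- Complementary log-log model by scheduled visit interval: about 2.0 in both cases.

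**Step 5, the replacements for the median.** Cumulative incidence at 36 and 60 months had 94-96% coverage with a half-width of 4-5 points; check: 1.96 × √(0.5 × 0.5/400) = 4.9 points. Read as visit intervals such as (36, 60], the same Kaplan-Meier limits covered the median in 98-100%.

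**The case against.** A reader might infer that the study will analyse regain by Kaplan-Meier and Cox. The documents do not say so. Regain above 15% at each visit is a repeated binary variable, for which the plan already names GLMM, GEE and logistic regression. The survival sentence may be meant only for revision surgery, where it is sound. This stands, and the point is therefore conditional. But the protocol does not exclude regain either, and it fixes the survival outputs before naming the event.

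Detail is deferred to a SAP. That also stands: this is a gap that can still be closed, not an error already made.

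The size depends on an incidence and onset pattern that no document supplies. This stands too. It would be wrong to say that the interval always misses or that the median is always far off. Below half crossing, there is nothing wrong with reporting that the median is not reached.

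One may add that true onset is not a protocol quantity, since weight is measured only at visits, and that regain need not be permanent. If the target is the first visit at which the threshold is exceeded, it is observed directly. It is then a visit category, better reported as incidence by visit than as a median in months.

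Finally, a reader might infer that choosing Efron is enough. It nearly is on nominal months, but not once visit dates vary, and it does nothing for the median.

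**Conclusion.** The point holds in conditional form, as a cheap improvement of low to moderate severity. The survival event is unnamed, and every follow-up outcome except revision surgery is seen only at visits up to 24 months apart. If one of those outcomes becomes the event and more than half of patients reach it by month 60, the reported median is a visit date, or close to one. It is roughly 3 to 18 months late in most patterns tried (1.5 to 22.3 across the table), with an interval that often excludes the true value. Cox hazard ratios are little affected when events are few, and shrink toward 1 when events are common. All these sizes rest on the assumed incidence, onset pattern and permanence of regain. The planned MMRM, GLMM, GEE and logistic analyses are unaffected, as is any survival analysis of revision surgery.

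**What to change.** In the SAP:

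- Name each survival event and its time origin; the date of surgery is available.
- Keep Kaplan-Meier and Cox for events with a recorded date, such as revision surgery.
- For events detected at visits, report cumulative incidence at 12, 36 and 60 months with 95% confidence intervals, or give the median only as a visit interval.
- For covariate effects on such events, use a discrete-time complementary log-log model with one intercept per scheduled visit interval, or an interval-censored model where visits are missed or dates vary. Do not rely on a tie option alone.

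The cost is SAP wording and a standard binary regression with a different link; no new data are collected. The downside is that times are reported by interval, with slightly more analysis work.
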